4.11 Immunogenicity Data

Immunogenicity data analysis will be described in a separate analysis plan.

4.12 Subgroup Analyses

As possible, subgroup analysis may be performed on key efficacy and safety data to evaluate the homogeneity of the treatment effect across main subject characteristics.

The following patient characteristics and subgroups will be considered:

- geographical region (Europe, North America),
- actual prior biological use (prior biological use, no prior biological use),
- actual weight category (≤ 90 kg, > 90 kg),
- actual prior biological use and weight category stratum derived from the observed values of body weight and prior biologic use at baseline,
- gender (female, male),
- geriatric status (< 65 , ≥ 65),
- PASI and/or IGA at baseline ($<$ median of baseline PASI score, \geq median of baseline PASI score and/or $<$ baseline IGA score of 4, \geq baseline IGA score of 4).

4.12.1 Variables

As feasible, subgroup analysis may be performed for the following efficacy variables in the ITT population and for the safety variables in the safety population:

Table 4.16: List of Efficacy Endpoints for Subgroup Analyses and Variables

	Endpoints	Type of Variables	Variables for Subgroup Analyses
Efficacy	IGA-derived endpoints	Binary	• proportion of subjects achieving an IGA score ≤ 1 and with an IGA reduction from baseline of 2 points or more at Weeks 12, 24, 36 and 48.
	PASI-derived endpoints	Categorical	• proportion of subjects achieving PASI 75/PASI 90/PASI 100 at Weeks 12, 24, 36 and 48.
		Continuous	• percent change from baseline in PASI score at Weeks 12, 24, 36 and 48.
Safety	Safety endpoint	Categorical	• number and percentage of subjects with AESI

In the next paragraphs, the analysis of the variables will be handled according to the type of variables or type of endpoint.

4.12.2 **Descriptive and Inferential Analyses**

4.12.2.1 **Binary and Categorical Variables**

The number and proportion of responders will be reported by treatment group and visit for each subgroup category and overall.

At each visit, proportions will be compared between treatment group using a logistic regression. The model will include the treatment and subgroup as categories as well as the treatment-by-subgroup interaction. The treatment-by-subgroup interaction will be tested at the 15% significance level. A forest plot will be produced for each endpoint and treatment comparison of interest. The following comparisons will be reported: pairwise comparison of each treatment arm to Plac/120mg (x4), Q4 at Weeks 12, 24, 36 and 48.

The forest plots will show the predicted proportions in each treatment group estimated from the models for each subgroup category and overall. Treatment comparisons will also be reported on the plots. Owing to the low sample size in the subgroups, some analyses may not be feasible. Further, no p-values will be produced, but the 95% confidence intervals on mean treatment ORs will be presented, if possible.

The calculated ORs in the forest plot for each stratum of the subgroup of combined prior biological use and weight category will also serve as the sensitivity analyses for the CMH tests of secondary efficacy analyses in case that the assumption of OR homogeneity was not met.

4.12.2.2 **Continuous Variables**

Each treatment comparison vs. placebo will be assessed using an ANCOVA with treatment, subgroup, the subgroup-by-treatment interaction as factors and the baseline value as a covariate in the model. Significance of the interaction will be tested at the 15% level. The LSM differences along with 95% CI for each pairwise comparison vs. placebo will be calculated at Week 12 in each category of the subgroup. This inferential analysis will be repeated for Weeks 24, 36 and 48.

The subgroup analysis of actual prior biological use and weight stratum will be used as sensitivity analyses of the secondary endpoints in case of some imbalance between the treatment groups that is solely due to chance, particularly if the imbalance is such that any M1095 groups may have a better prognosis than the control group. This will assess the robustness of the conclusions drawn from the secondary analyses based on the ANCOVA analysis. Additional analyses may be performed to adjust for other baseline covariates if deemed necessary.

A forest plot displaying the LSM differences and the 95% CI in each category of subgroups will be produced for each pairwise treatment comparison. The p-value of the treatment-by-subgroup interaction will also be displayed and tested at the 15% level.

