4.2.1.3 Inferential Analyses

The IGA responder rates at Week 12 will be compared between treatment groups using CMH test stratified by actual prior use of biologic therapy (yes/no) and body weight stratum (≤ 90 kg, > 90 kg) as observed at baseline. The following four null hypotheses will be individually tested at the unadjusted two-sided 5% significance level:

- H₁: M1095 30 mg Q2W × 3, followed by 30 mg Q4W × 1, is not different from placebo with respect to achievement of IGA response,
- H₂: M1095 60 mg Q2W × 3, followed by 60 mg Q4W × 1, is not different from placebo with respect to achievement of IGA response,
- H₃: M1095 120 mg Q2W × 3, followed by 120 mg Q4W × 1, is not different from placebo with respect to achievement of IGA response,
- H₄: M1095 120 mg Q2W × 6 is not different from placebo with respect to achievement of IGA response

resulting in the following comparisons at Week 12 between the treatment groups/regimens:

- | | | |
|---|---|---|
| 
 • M1095 30 mg wk 0, 2, 4, 8 • M1095 60 mg wk 0, 2, 4, 8 • M1095 120 mg wk 0, 2, 4, 8 • M1095 120 mg wk 0, 2, 4, 6, 8, 10 | } | vs. placebo wk 0, 1, 2, 3, 4, 6, 8, 10. |
|---|---|---|

The CMH Odds Ratio (OR) for the comparison of each M1095 treatment arm to placebo will be presented along with its 95% CI and associated p-value.

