4.2.2.2.3 Continuous Variables

The raw PASI score, absolute change and percent change from baseline in PASI score will be presented by treatment group and over time for all visits up to Week 52 using summary statistics and listings. Mean of change from baseline in PASI and its associated standard error will be displayed graphically over time by treatment group.

For the percent change in PASI, treatment comparisons vs. placebo and between M1095 treatment groups will be tested at each specified visit up to Week 48. The treatment LSM along with the corresponding SE, 95% CI and the LSM differences along with its SE, 95% CI and p-value will be obtained at each visit separately using an analysis of covariance (ANCOVA) model. The ANCOVA will include the planned treatment group, actual prior biologic and weight stratum as factors and the baseline value as a covariate. The residuals from the ANCOVA model will be examined to check that the assumptions of normality, independence and homoscedasticity hold.

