4.12.2.3 Safety Variables

The number and percentage of subjects with AESI will be summarized by treatment group classed by SOC and PT for each category of the subgroup for the induction and overall period (refer to Section 4.9.2.5).

REDACTED COPY

This document must not be used to support any marketing authorization application or any variation or extension of such application

5 Sample Size Calculation

A sufficient number of subjects will be screened, so that a total of approximately 300 subjects will be randomized (approximately 50 per treatment group).

With this sample size, the study has > 99% power to detect a statistically significant difference between any treatment arm and placebo in the IGA score of 0 or 1 rate at Week 12, with a two-sided, unadjusted type I error of 0.05. These calculations assume IGA score of 0 or 1 rates of > 88% for study drug and \leq 7% for placebo. As this is a phase 2 study, there will be no adjustments for multiplicity.

Exploratory analyses between the different dose levels of M1095 will also be performed. The PASI 100 response rate offers more discriminatory potential for this. Phase 1 data and response simulations give a PASI 100 response rate at Week 12 varying from 45 to 72%. With the sample size of 50 subjects per group, based on these assumed PASI 100 response rates at Week 12, the comparison between the highest and lowest M1095 doses has approximately 79% power.

Power calculations have been performed with SAS v.9.4 Proc Power using the methodology for a two-group chi square test of equal proportions.

Randomization will be stratified by prior biologic use (yes, no) and weight (\leq 90 kg, > 90 kg).

6 Reference List

Abraha, Iosief & Montedori, Alessandro. (2010). Modified intention to treat reporting in randomised controlled trials: Systematic review. *BMJ (Clinical research ed.)*. 340. c2697. 10.1136/bmj.c2697.

Committee for Medicinal Products for Human Use, 2017. Guideline on immunogenicity assessment of therapeutic proteins. London: European Medicines Agency.

Committee for Proprietary Medicinal Products (CPMP), Points to Consider on Adjustment for Baseline Covariates (2003). *Stat Med*, 23(5), pp.701-709.

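### The subgroup ANCOVA for percent change in PASI leaves out the two randomization factors that the main ANCOVA adjusts for, at a small and avoidable cost in precision

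*SAP*

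**What the plan says.** SAP Section 5 and protocol 9.2 fix the design: "Randomization will be stratified by prior biologic use (yes, no) and weight", with weight cut at 90 kg.

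The main analysis of percent change in PASI (SAP 4.2.2.2.3) carries both factors: "The ANCOVA will include the planned treatment group, actual prior biologic and weight stratum as factors and the baseline value as a covariate". Protocol 9.4.1 describes the same model. The primary and secondary binary comparisons use a CMH test stratified by the same two factors (SAP 4.2.1.3 and 4.2.2.2.1).

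The subgroup analysis of the same continuous endpoint (SAP 4.12.2.2) is done "using an ANCOVA with treatment, subgroup, the subgroup-by-treatment interaction as factors and the baseline value as a covariate in the model". It gives LSM differences from placebo with 95% intervals at Weeks 12, 24, 36 and 48, tests the interaction at the 15% level and prints its p-value on the plot. The plot is described as "A forest plot displaying the LSM differences and the 95% CI in each category of subgroups".

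The subgroups in SAP 4.12 are region, prior biologic use, weight category, gender, geriatric status, baseline PASI and/or IGA, and "actual prior biological use and weight category stratum derived from the observed values of body weight and prior biologic use at baseline".

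The subgroup logistic model for the binary endpoints (SAP 4.12.2.1) is similarly sparse: "The model will include the treatment and subgroup as categories as well as the treatment-by-subgroup interaction".

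**The concern.** Factors used to stratify the randomization are normally kept in the model, and this SAP keeps them in its other ANCOVA comparisons, including quality of life (4.3.2). The subgroup ANCOVA is the exception, and no reason is given.

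Two things follow for percent change in PASI. First, any outcome variation due to weight or prior biologic use stays in the error term, so the LSM-difference intervals are wider and the interaction test weaker than they need be. Second, stratification balances the two factors across whole arms but does not guarantee balance within, say, women or North American subjects. SAP 4.12.2.2 itself worries about chance imbalance that favours the M1095 arms, yet most of its subgroup models cannot correct for imbalance in these two factors.

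What is at stake is the sharpness of an optional, supportive analysis. No primary or secondary conclusion depends on it.

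**Working it through.** **The plan's own figures.** For PASI 100 at 45% vs 72% with 50 per arm and two-sided 0.05, the mean rate is 0.585. The pooled SE is sqrt(2 × 0.585 × 0.415 / 50) = 0.0985 and the unpooled SE is sqrt((0.2475 + 0.2016) / 50) = 0.0948. So z = (0.27 − 1.96 × 0.0985) / 0.0948 = 0.81, and power is 79%, as stated. The figure of over 99% for IGA also reproduces. Neither depends on the subgroup models, so they confirm the inputs but do not bear on this point.

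**Which factors are missing from the subgroup ANCOVA**

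| Subgroup | Prior biologic use | Weight category |
|---|---|---|
| Region, gender, geriatric status, baseline PASI/IGA | missing | missing |
| Weight category | missing | present |
| Prior biologic use | present | missing |
| Combined stratum | present | present |

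**Precision.** Let R² be the share of residual variance, after the terms already in the model, that the two factors explain. To first order, SE without the factors / SE with them = 1 / sqrt(1 − R²). The same ratio applies to the subgroup differences and to the interaction contrasts.

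This was checked by simulation: six arms of 50, block randomization within strata, and 1,500 trials per R². Assumed prevalences were 30% prior biologic use, 45% above 90 kg and 35% in the subgroup, with a true effect of 1.5 SD.

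| R² (assumed) | Formula | Simulated ratio of model SEs |
|---|---|---|
| 0 | 1.000 | 0.998 |
| 2% | 1.010 | 1.007 |
| 5% | 1.026 | 1.024 |
| 10% | 1.054 | 1.054 |
| 20% | 1.118 | 1.118 |

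Mean estimates lay between 1.48 and 1.52 with and without the factors, so neither model is biased. If the factors are worthless, adding them costs about 0.2% in SE.

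The actual spread of the estimates differed by less than the model SEs at the top of the range. At R² = 20% the empirical SDs were 0.327 and 0.311, a ratio of 1.05, while the unadjusted model SE averaged 0.344. Part of the excess width is therefore the unadjusted model failing to credit the balance that stratification already gives. Its intervals are slightly conservative.

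For scale, R² near 10% corresponds to effects of 0.6 SD for weight and 0.3 SD for prior biologic use with even splits: 0.25 × (0.36 + 0.09) = 0.1125, and 0.1125 / 1.1125 = 10.1%.

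**Imbalance within a subgroup.** Assume half of each arm of 50 is above 90 kg, stratification holds this at 25 of 50 in both arms, and the subgroup takes 25 per arm. The number above 90 kg in the subgroup is then hypergeometric. The variance of the share in one arm is (0.25 / 25) × (25 / 49) = 0.0051. The between-arm SD is sqrt(2 × 0.0051) = 0.101, or about 10 percentage points. With a weight effect of 0.6 SD, a one-SD imbalance shifts the subgroup difference by 0.101 × 0.6 = 0.06 SD. The SE of that difference is about sqrt(2 / 25) = 0.28 SD.

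**The logistic model.** At 45% vs 72%, the log-OR SE without the factors is sqrt(1/12.375 + 1/10.08) = 0.424. At 7% vs 88% it is sqrt(1/3.255 + 1/5.28) = 0.705. With the prevalences above and assumed stratum odds ratios of 2, adding the factors raises these SEs to 0.438 and 0.756, and moves the ORs from 3.14 to 3.34 and from 97 to 116. At a 7% placebo rate, a cell of 25 has no responder with probability 0.93^25 = 16%, and a cell of 10 with probability 0.93^10 = 48%.

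**The case against.** The best defence is that little is lost and nothing is contradicted. Protocol 9.4.6 leaves subgroup methods to the SAP, the subgroup analyses are worded as optional, and the combined-stratum subgroup model contains both factors. SAP 4.12.2.2 assigns that model to chance imbalance and permits further covariate adjustment. The gain depends on prognostic strength that the documents do not give. All of this stands as a limit on size. It does not remove the point. The combined-stratum model says nothing about imbalance within region, gender, age or severity subgroups, and the permission to adjust further is discretionary and does not name these factors.

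A reader might infer more than the documents support, in four ways:

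- **That the logistic subgroup intervals are also too wide.** The reverse holds. Leaving out the factors lowers the log-OR SE and pulls the OR toward 1, because conditional and marginal odds ratios differ. Most efficacy variables in Table 4.16 are binary (IGA response and PASI 75/90/100), so the precision argument covers only percent change in PASI.
- **That an overall row on the continuous plot will disagree with the main result.** No such row is stated. Overall estimates are described only for the binary plots: "The forest plots will show the predicted proportions in each treatment group estimated from the models for each subgroup category and overall".
- **That weight imbalance within a subgroup has an SD of 14 points**, from sqrt(2 × 0.25 / 25) = 0.141. That ignores the stratification; about 10 points is right.
- **That the subgroup estimates are biased.** On average they are not.

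**Conclusion.** The point holds for the subgroup ANCOVA of percent change in PASI, as a minor improvement. The model omits one or both randomization factors in every subgroup except the combined stratum, although the main ANCOVA for the same endpoint includes them. The cost is an SE about 0 to 5% larger if the factors explain up to 10% of residual variance, and 12% larger at 20%. Chance weight imbalance with an SD of about 10 percentage points in a half-size subgroup is also left uncorrected.

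These sizes rest on assumed values: R² of 0 to 20%, half the subjects above 90 kg for the imbalance figure, and the stated prevalences for the simulation. The omission itself rests on the text alone. It does not make the intervals invalid (they err slightly wide), does not conflict with the protocol, and does not extend to the logistic model as a precision fault.

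**What to change.** In SAP 4.12.2.2, state that each subgroup ANCOVA also includes actual prior biologic use and actual weight category as factors, omitting whichever factor or factors define the subgroup. This brings the covariates into line with 4.2.2.2.3.

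The cost is one sentence and at most two model terms, both already needed for the main ANCOVA. In a six-arm model, residual degrees of freedom fall from 300 − 13 = 287 to 285. Table 2.1 lists subgroup analyses for the second interim analysis, so the change is best made before the unblinding for that analysis.

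Do not require the same terms in the logistic model of 4.12.2.1. There they raise the log-OR SE and the risk of separation in sparse cells, and the SAP already warns that some of those analyses may not be feasible.

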4.12.2.3 Safety Variables

The number and percentage of subjects with AESI will be summarized by treatment group classed by SOC and PT for each category of the subgroup for the induction and overall period (refer to Section 4.9.2.5).

REDACTED COPY

This document must not be used to support any marketing authorization application or any variation or extension of such application

5 Sample Size Calculation

A sufficient number of subjects will be screened, so that a total of approximately 300 subjects will be randomized (approximately 50 per treatment group).

With this sample size, the study has > 99% power to detect a statistically significant difference between any treatment arm and placebo in the IGA score of 0 or 1 rate at Week 12, with a two-sided, unadjusted type I error of 0.05. These calculations assume IGA score of 0 or 1 rates of > 88% for study drug and \leq 7% for placebo. As this is a phase 2 study, there will be no adjustments for multiplicity.

Exploratory analyses between the different dose levels of M1095 will also be performed. The PASI 100 response rate offers more discriminatory potential for this. Phase 1 data and response simulations give a PASI 100 response rate at Week 12 varying from 45 to 72%. With the sample size of 50 subjects per group, based on these assumed PASI 100 response rates at Week 12, the comparison between the highest and lowest M1095 doses has approximately 79% power.

Power calculations have been performed with SAS v.9.4 Proc Power using the methodology for a two-group chi square test of equal proportions.

Randomization will be stratified by prior biologic use (yes, no) and weight (\leq 90 kg, > 90 kg).

6 Reference List

Abraha, Iosief & Montedori, Alessandro. (2010). Modified intention to treat reporting in randomised controlled trials: Systematic review. *BMJ (Clinical research ed.)*. 340. c2697. 10.1136/bmj.c2697.

Committee for Medicinal Products for Human Use, 2017. Guideline on immunogenicity assessment of therapeutic proteins. London: European Medicines Agency.

Committee for Proprietary Medicinal Products (CPMP), Points to Consider on Adjustment for Baseline Covariates (2003). *Stat Med*, 23(5), pp.701-709.

7.1 Appendix A: Scoring of DLQI

The Dermatology Life Quality Index (DLQI) includes 10 items related to general dermatology disability to assess health-related quality of life in adults with skin disease. It includes several domains of daily activities, leisure, personal relationships, symptoms and feelings, treatment, and work/school (Finlay & Khan, 1994).

[REDACTED]

[REDACTED]

- 1. [REDACTED]
- 2. [REDACTED]
- 3. [REDACTED]
- 4. [REDACTED]
- 5. [REDACTED]
- 6. [REDACTED]

[REDACTED]

[REDACTED]	[REDACTED]	[REDACTED]
[REDACTED]	[REDACTED]	[REDACTED]
[REDACTED]	[REDACTED]	[REDACTED]
[REDACTED]	[REDACTED]	[REDACTED]
[REDACTED]	[REDACTED]	[REDACTED]
[REDACTED]	[REDACTED]	[REDACTED]
[REDACTED]	[REDACTED]	[REDACTED]

There will be no missing items since this questionnaire is handled using an electronic tablet device.

The minimal clinically important difference of the DLQI is determined as a change in DLQI score of at least 4 points (Basra et al, 2015).

7.2 Appendix B: Derivation of EQ-PSO

EQ-PSO, based on EQ-5D-3L, is a generic instrument to assess the health status of subjects suffering from psoriasis. This instrument comprises 7 dimensions: mobility, self-care, usual activities, pain/discomfort, anxiety/depression, skin irritation and self-confidence, the last two being the two psoriasis-specific dimensions. For each dimension, there will be 3 response levels: no problems, some problems and severe problems coded as follows:

- Level 1 or “no problems”: coded as 1
- Level 2 or “some problems”: coded as 2
- Level 3 or “severe problems”: coded as 3.

The EQ-PSO (VAS) based on vertical VAS is a score ranging from 0 to 100 (in mm), with 0 being the worst imaginable health state and 100 the best imaginable health state. An improvement in EQ-PSO will be described by a positive change from baseline since a higher score at a post-baseline visit indicates a better subject’s health status.

7.3 Appendix C: Scoring of SF-36 (Version 2 Standard)

The SF-36v2® Health Survey Scoring Software (Optum® PRO CoRE Software Version 1.2) will be employed to calculate the SF-36v2® 8-domain scales and 2-component summary measures (Ware et al., 2011). The SF-36, a 36-item questionnaire completed by the subject, is designed to describe and monitor the health of subjects in terms of health domain scales:

[REDACTED]

In addition, the Physical and Mental Component Summary (PCS and MCS) scores that aggregate all health domain scales will respectively give an assessment of the physical and mental wellbeing of subjects. Each domain scale and summary score will be directly transformed into a 0-100 scale before being standardized, with lower scores indicating more disability and higher scores less disability. In this study, the scoring will be based on the SF-36v2 standard version that has a 4-week recall period.

The process for scoring SF-36v2 health domain scales and component summary measures with the help of the scoring software is described below (Ware et al., 2011):

- [REDACTED]

[REDACTED]	[REDACTED]
[REDACTED]	[REDACTED]
[REDACTED]	[REDACTED]
[REDACTED]	[REDACTED]
[REDACTED]	[REDACTED]
[REDACTED]	[REDACTED]

- [REDACTED]

- [REDACTED]

- [REDACTED]

[REDACTED]	[REDACTED]	[REDACTED]	[REDACTED]
[REDACTED]	[REDACTED]	[REDACTED]	[REDACTED]
[REDACTED]	[REDACTED]	[REDACTED]	[REDACTED]
[REDACTED]	[REDACTED]	[REDACTED]	[REDACTED]
[REDACTED]	[REDACTED]	[REDACTED]	[REDACTED]
[REDACTED]	[REDACTED]	[REDACTED]	[REDACTED]

This document must not be used for any variation or extension of this application

[REDACTED]	[REDACTED]	[REDACTED]
[REDACTED]	[REDACTED]	[REDACTED]
[REDACTED]	[REDACTED]	[REDACTED]
[REDACTED]	[REDACTED]	[REDACTED]
[REDACTED]	[REDACTED]	[REDACTED]
[REDACTED]	[REDACTED]	[REDACTED]
[REDACTED]	[REDACTED]	[REDACTED]

[REDACTED]	[REDACTED]	[REDACTED]	[REDACTED]
[REDACTED]	[REDACTED]	[REDACTED]	[REDACTED]
[REDACTED]	[REDACTED]	[REDACTED]	[REDACTED]
[REDACTED]	[REDACTED]	[REDACTED]	[REDACTED]
[REDACTED]	[REDACTED]	[REDACTED]	[REDACTED]
[REDACTED]	[REDACTED]	[REDACTED]	[REDACTED]
[REDACTED]	[REDACTED]	[REDACTED]	[REDACTED]
[REDACTED]	[REDACTED]	[REDACTED]	[REDACTED]
[REDACTED]	[REDACTED]	[REDACTED]	[REDACTED]
[REDACTED]	[REDACTED]	[REDACTED]	[REDACTED]
[REDACTED]	[REDACTED]	[REDACTED]	[REDACTED]
[REDACTED]	[REDACTED]	[REDACTED]	[REDACTED]
[REDACTED]	[REDACTED]	[REDACTED]	[REDACTED]
[REDACTED]	[REDACTED]	[REDACTED]	[REDACTED]
[REDACTED]	[REDACTED]	[REDACTED]	[REDACTED]

- [REDACTED]
- [REDACTED]
- [REDACTED]
- [REDACTED]
- [REDACTED]
- [REDACTED]

This document may not be reproduced, stored in a retrieval system, or transmitted in any form or by any means, electronic, mechanical, photocopying, recording, or by any information storage and retrieval system, without the prior written permission of the sponsor. This document may not be used for marketing, promotional, or other purposes without the prior written permission of the sponsor. This document may not be used for marketing, promotional, or other purposes without the prior written permission of the sponsor.

[REDACTED]

- [REDACTED]

- [REDACTED]

- [REDACTED]

REDACTED COPY

This document must not be used to support any marketing authorization application or any variation or extension of such application

